### **Unanticipated Adverse Device Effect (UADE)/Unanticipated Serious Adverse Device Effect (USADE)**

Any UADE (USA 21CFR 812.3(s)) or USADE (ISO 14155) is defined as any serious adverse effect on health or safety or any life-threatening problem or death caused by, or associated with, a device, if that effect, problem or death was not previously identified in nature, severity, or degree of incidence in the investigational plan (i.e., this protocol), application (including a supplementary plan or application), or risk assessment, or any other unanticipated serious problem associated with a device that relates to the rights, safety, or welfare of subjects.

### **Serious Health Threat**

A serious health threat (following ISO 14155) is a signal from any adverse event or device deficiency that indicates an imminent risk of death or a serious deterioration in the health in subjects, users or other persons, and that requires prompt remedial action for other subject, users or other persons. This would include events that are of significant and unexpected nature such that they become alarming as a potential serious health hazard or possibility of multiple deaths occurring at short intervals.

## 11.2 PRODUCT COMPLAINT/DEVICE DEFICIENCY DEFINITION

A product complaint/device deficiency is defined (21 CFR 820.3(b) and ISO 14155) as any alleged deficiency related to the identity, quality, durability, reliability, safety, effectiveness, or performance of a device. This may include malfunctions, use error, and inadequacies in labeling. Product complaints can pertain to any marketed JJSV device being used in the study. The investigator is to assess whether the deficiency could have led to a serious adverse event without suitable action or intervention or under less fortunate circumstances.

## 11.3 ADVERSE EVENT AND COMPLAINT REPORTING REQUIREMENTS

All adverse events and any complaint encountered using any JJSV product, regardless of severity and whether attributed to the study device(s), are to be reported to JJSV and recorded on the case report form corresponding to the visit during which awareness of the event occurred. Adverse events are also to be reported to the reviewing IEC/IRB as per the IEC's reporting requirements. If required, adverse events will be reported to the appropriate regulatory agencies (e.g., FDA/Health Canada) according to all applicable laws and regulations. Specific instructions on notification procedures to JJSV are included in **Appendix I**, Adverse Event Reporting.

Reporting of adverse events shall follow the USA Code of Federal Regulations (21CFR812) for sites in the USA. For sites located outside the USA, reporting of adverse events shall follow ISO 14155 and country-specific guidelines, of which the shortest/strictest timeline requirement for reporting adverse events will be followed. General guidelines are provided below:

### Adverse Event Reporting

An adverse event that is not serious or device-related is to be reported to JJSV in a timely manner. Notification of non-serious and non-device related adverse events will occur by recording events on the CRF when noted. Such adverse events are also to be reported to the reviewing IEC/IRB per their reporting requirements.

### Complaints/Device Deficiency Reporting

A general product complaint or device deficiency is to be reported to JJSV in a timely manner. Notification of complaints/device deficiencies will occur by recording complaints on the CRF at the visit the complaint occurs (e.g., operative visit) and/or by a phone call/email to JJSV.

[REDACTED]

If an adverse event is believed to be definitely, probably or possibly related to the study device and/or the use of the device, the event will be considered related to the study device and/or the use of the device.

### 11.5 ADVERSE EVENT FOLLOW-UP

For every adverse event, appropriate measures should be undertaken to treat and/or monitor the subject until resolution occurs. Obtain and maintain in the subject's files all pertinent medical data relating to the event including the subject's medical records, medical reports and/or judgments from colleagues or outside specialists who assisted in the treatment and follow-up of the subject.

[REDACTED]

[REDACTED] Any subject who is exited from the study due to a serious and/or device-related adverse event will be followed until the outcome is determined.

## 12. PROTOCOL CHANGES/AMENDMENTS

If the investigator wishes to modify any procedure and/or the design of the study, he or she must contact and obtain consent from JJSV regarding the proposed changes prior to implementation. Any modifications (including additional data collection) require approval by the governing IEC/IRB prior to implementation.

## 13. ETHICS REVIEW AND PATIENT WELFARE

### 13.1 INDEPENDENT ETHICS COMMITTEE/INSTITUTIONAL REVIEW BOARD (IEC/IRB)

It is the responsibility of the investigator to obtain prospective approval of the study protocol, protocol amendments or changes, informed consent forms (ICF), and other relevant documents (e.g., advertisements) from the IEC/IRB. All correspondence with the IEC/IRB should be retained in the Investigator Study Files/Notebook. Copies of IEC submissions and approvals should be forwarded to JJSV.

The investigator is responsible for notifying the IEC/IRB of reportable adverse events as well as any other circumstance in which additional procedures outside the protocol were conducted to eliminate apparent hazards to subjects.

### 13.2 INFORMED CONSENT

The current version of the IEC/IRB-approved study ICF must be signed by each study subject prior to any study-specific examinations being performed. The IEC/IRB-approved ICF is to be signed and dated by the subject as well as by the person who conducted the informed consent discussion. The signed ICF will be maintained by the investigator as a permanent part of the subject's medical records. A copy of the signed and dated form is to be provided to the subject. The investigator will provide JJSV written acknowledgement on the preoperative case report form that a signed agreement of informed consent has been obtained and is in the investigator's possession for each

subject. As required by 21CFR812 Part G, the site shall document in the patient chart that informed consent was obtained prior to participation in the study for each subject enrolled.

**NOTE:** *The informed consent process also includes obtaining the subject's signature on an Authorization for Use/Disclosure of Health Information for Research Form or equivalent documentation necessary to comply with applicable privacy laws pertaining to medical treatment in the governing countries.*

**NOTE:** *The sponsor will secure appropriate insurance for study subjects prior to study start.*

## **14. DOCUMENTATION**

### **14.1 SOURCE DOCUMENTS**

Source documents must be kept for all study subjects. Source documents may include a subject's medical records, hospital charts, clinic charts, the investigator's subject study files, as well as results of any diagnostic tests or procedures such as topographies or laboratory tests with photographs or instrument printouts.

Each site is expected to adhere to the clinic's own standard documentation requirements for medical charts/clinic notes. For the purposes of this clinical study, the medical charts/clinic notes must also include, at a minimum, the following data that will be considered source data and will be reviewed by the Sponsor:

- Subject's name and study identification number
- Subject's contact information
- Study protocol number and the Sponsor name (JJSV)
- A statement that informed consent was obtained prior to participation in the study (including the date)
- Evidence of subject eligibility
- Dates of all subject visits and surgeries throughout the duration of the study
- Implant serial number identification (NOTE: This is masked information, and may only be reviewed by unmasked study staff)
- Concurrent medications
- Corrected and uncorrected distance visual acuity (NOTE: ETDRS visual acuity score cards are considered source documentation and are to be retained by the site in the subject CRF notebooks)
- Manifest refraction
- Occurrence and status of any operative complications, postoperative medical or lens findings and adverse events
- Occurrence and status of any subject complaints, e.g., ocular/visual symptoms
- The date the subject exited the study, and a notation as to whether the subject completed the study or reason for early exit.

[REDACTED]

### 15.2 ADMINISTRATIVE MONITORING

Administrative monitoring procedures will ensure that study devices, subjects, and forms can be traced and will allow monitoring of investigator progress and compliance.

Accountability and traceability of study devices will be monitored by trained JJSV personnel.

[REDACTED]

[REDACTED]

[REDACTED]

[REDACTED]

[REDACTED]

[REDACTED]

[REDACTED]

[REDACTED]

[REDACTED]

## 16. MEDICAL OVERSIGHT

The medical monitor will be available throughout the clinical trial to review study results and to answer any questions from investigators. The medical monitor will review and assess any reports of serious and/or device-related adverse events and discuss these with the reporting investigator(s) as necessary. The medical monitor, as well as any other qualified personnel designated by JJSV, shall also review study reports.

## 17. PUBLICATIONS

[REDACTED]

## 18. RISK ANALYSIS

### POTENTIAL RISKS AND RISK MANAGEMENT

#### RISKS OF THE STUDY LENSES

The risks and benefits of the commercially available TECNIS Eyhance Toric II IOL, TECNIS Synergy Toric II IOL, and the TECNIS Toric 1-Piece IOL are detailed in their respective approved product labeling (i.e., Directions for Use).

#### GENERAL RISKS OF CATARACT SURGERY AND IOL IMPLANTATION

There are risks and complications associated with cataract surgery and IOL implantation in general. These can include worsening of vision, hemorrhage, loss of corneal clarity, inflammation, infections, retinal detachment, pupil changes, glaucoma, etc. Complications can result in poor vision, loss of vision or loss of the eye.

#### RISK MANAGEMENT

Subjects will be closely monitored throughout the trial duration. The occurrence of adverse events and complaints will be assessed at each study visit and reported to JJSV according to **Section 11.0**, Adverse Events and Product Complaints. Additionally, JJSV will monitor incoming data following the procedures outlined in **Section 15.0**, Monitoring. The Medical Monitor will ensure subjects are not exposed to additional risks by monitoring serious adverse events, device-related adverse events, and device-deficiencies that could have led to serious adverse events (**Section 16.0**, Medical Oversight).

#### POTENTIAL BENEFITS

The primary benefit from implantation of either of the study lens models is the correction of aphakia and corneal astigmatism following removal of the natural crystalline lens due to cataract.

CONCLUSION

The hazards/risks associated with either of the study lens models are expected to be acceptable and within those of currently marketed IOLs. These IOLs have been approved for market based on the determination that the potential benefits outweigh the residual risks when the devices are used as intended.

**19. RECORDS RETENTION**

All study-related correspondence, subject records, consent forms, Authorization for Use/Disclosure of Health Information Forms or similar medical treatment privacy law documentation, records of the distribution and use of all study products, and original case report forms should be maintained by the investigator.

[REDACTED]

[REDACTED]

- [REDACTED]
- [REDACTED]
- [REDACTED]
- [REDACTED]
- [REDACTED]
- [REDACTED]
- [REDACTED]
- [REDACTED]
- [REDACTED]
- [REDACTED]
- [REDACTED]
- [REDACTED]
- [REDACTED]

**20. TERMINATION OF THE STUDY**

The clinical study will be suspended in the event of high levels of complications and/or adverse events that are unexpected in nature and/or severity and evaluated as to causality relative to the study device. The clinical study may be suspended if the Medical Monitor or IEC/IRB, upon review and evaluation of the clinical data, finds unacceptable clinical performance or the level of single or total complications and/or adverse events unacceptable for continuation of the study.

If causality is shown not to be related to the device, the study may be resumed in accordance with the IEC/IRB. The study will be terminated if causality is shown to be related to the study device.

Additionally, the investigator, or JJSV may stop a subject's participation at any time. JJSV may also stop the study at any time for reasons it determines appropriate; however, no suspension of the study would be made to disadvantage the study subjects. Following suspension of the study for any reason, all study subjects who have already received treatment would continue to be followed through completion of the study visit schedule.

## 21. STATISTICAL METHODS

This section highlights the analyses to be performed for key study endpoints. The detailed analysis plan will be documented in the Statistical Analysis Plan (SAP). Data from the [REDACTED] postoperative visit will be the key timeframe for rotational stability [REDACTED]

[REDACTED]

[REDACTED] All complications and adverse events will be evaluated at all visits.

Summary statistics include mean, standard deviation, median, minimum, and maximum for continuous variables, and frequency counts and proportions for categorical endpoints. [REDACTED]

[REDACTED]

[REDACTED]

### 21.1 ANALYSIS POPULATIONS

[REDACTED]

- All Implanted Safety population: all subjects randomized and bilaterally or unilaterally implanted with test or control lens and analyzed per treatment received. All eyes will include both study eyes from bilaterally implanted subjects and one study eye from unilaterally implanted subjects.

[REDACTED]

### 21.2 Effectiveness Endpoints

All analyses will be based on observed case available data at each study visit with no imputation of missing data, [REDACTED].

#### Primary Endpoint

The primary endpoint is the percentage of eyes with rotational stability of the IOL at postoperative [REDACTED] (i.e., misalignment  $\leq 10^\circ$  at the [REDACTED] visit relative to baseline).

[REDACTED]

[REDACTED]

[REDACTED]

[REDACTED]

[REDACTED]

[REDACTED]

[REDACTED]

[REDACTED]

[REDACTED]

[REDACTED]

[REDACTED]

[REDACTED]

[REDACTED]

[REDACTED]

[REDACTED]

[REDACTED]

[REDACTED]

[REDACTED]

[REDACTED]

[REDACTED]

[REDACTED]

For the rotational stability endpoint, the primary analysis population will be All Implanted Safety population. [REDACTED]

[REDACTED]

[REDACTED]

[REDACTED]

[REDACTED]

#### Other Effectiveness Endpoints

All statistical descriptive summaries for all other timepoints will be presented by lens group. [REDACTED]

[REDACTED]

[REDACTED]

**21.3 SAFETY AND OTHER ENDPOINTS**

ADVERSE EVENTS

The frequency counts and proportion of eyes with medical/lens findings or adverse events will also be reported by lens group.

[REDACTED]

**21.4 VISUAL ACUITY CONVENTIONS AND STATISTICS**

Visual acuity data will be converted to LogMAR values prior to analysis and adjusted for the test distance used if it is not the standard distance for the chart. Summary statistics will include sample size (N), mean, standard deviation (SD), median, minimum (Min), maximum (Max), [REDACTED] as appropriate [REDACTED]

[REDACTED]

## 22. FUNDING

The funding of this clinical trial will be provided by the sponsor, Johnson & Johnson Vision, [REDACTED].

1 INTRODUCTION

This document summarizes the statistical methods for the safety and effectiveness analyses of the JJSV201EYST study, comparing the TECNIS Eyhance® Toric II IOL and the TECNIS Synergy® Toric II IOL to the TECNIS Toric 1-Piece IOL. [REDACTED]

[REDACTED] Prospective, multi-center, three-arm, randomized, controlled study conducted at up to 20 sites located in North America [REDACTED]

[REDACTED] Subjects will be randomized to a treatment group (masked) in ratio 1:1:1 of the three treatments. [REDACTED]

The sponsor has decided to terminate the study early. [REDACTED]

[REDACTED] Due to a much smaller sample size than planned, only descriptive summaries of safety and selected effectiveness endpoints will be presented. All implanted subjects will be followed to at least 1-month postoperative.

1.1 STUDY OBJECTIVES

The purpose of this clinical study was to compare the performance outcomes of eyes implanted with the TECNIS Eyhance® Toric II IOL and the TECNIS Synergy® Toric II IOL to the TECNIS Toric 1-Piece IOL (control) [REDACTED]

1.2 SELECTED STUDY ENDPOINTS

- Rotational stability

■ [REDACTED]

■ [REDACTED]

- Adverse events

1.3 STUDY HYPOTHESES

1.4 RANDOMIZATION AND MASKING

A randomization list will be created [REDACTED]
Subjects will be randomized to either the test #1, test #2, or control IOL on a 1:1:1 basis. Randomization will take place after the subject has signed the informed consent document, has met all inclusion and exclusion criteria, and the investigator has documented which eye will be the first implanted (if bilaterally enrolled).

The subjects and the study technicians performing the postoperative vision tests are to be masked through study completion. [REDACTED]

[REDACTED]

2 ANALYSIS POPULATIONS AND GENERAL STATISTICS

2.1 ANALYSIS POPULATIONS

- All Implanted Safety population: all subjects randomized and bilaterally or unilaterally implanted with test or control lens and analyzed per treatment received. All eyes will include both study eyes from bilaterally implanted subjects and one study eye from unilaterally implanted subjects.

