## 10. EXPERIMENTAL PLAN

### 10.1 OVERVIEW

This study will be conducted in accordance with U.S. Code of Federal Regulations the Declaration of Helsinki, ISO 14155:2020 and all other applicable laws and regulations. The study will not begin until IRB/IEC approval has been obtained.

This study will be a prospective, three-arm, randomized, controlled clinical study conducted at up to 20 study sites located in North America. [REDACTED]

[REDACTED] After informed consent is obtained and all eligibility criteria are confirmed as being met, the subject (one or both eyes) may be enrolled and randomized to a treatment group.

For subjects with both eyes eligible, the investigator will choose which eye to operate on first at his/her discretion and standard clinical practice (e.g., the eye with the worse cataract, poorer best corrected distance vision and/or more severe optical/visual complaints); both eyes will be implanted with the same lens model. [REDACTED]

The study visits and procedures will include procedures that are study-specific or part of normal clinical practice, [REDACTED]

[REDACTED] The operative visit procedures for the study will be standard procedures for cataract surgery and IOL implantation.

Key postoperative assessments include IOL axis measurement [REDACTED]

[figure not shown]

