2.4 DATA CONVENTIONS

Descriptive statistics will typically include sample size (N), mean, standard deviation (SD), median, minimum (Min.), and maximum (Max.) as appropriate for continuous variables. For categorical data, the frequency and proportion will be computed.

For visual acuity data, data will be converted to LogMAR prior to analysis. [REDACTED]

[REDACTED]

[REDACTED]

[REDACTED]

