5 DEFINITION AND ANALYSIS OF SELECTED EFFECTIVENESS AND SAFETY ENDPOINTS

ROTATIONAL STABILITY

The absolute axis rotation compared to operative visit will be reported at all postoperative visits collected. The frequency counts and proportion of eyes with [REDACTED] $\leq 10^\circ$, [REDACTED] of axis change at all postoperative visits will be reported by lens group.

[REDACTED]

[REDACTED]

[REDACTED]

[REDACTED]

[REDACTED]

[REDACTED]

ADVERSE EVENTS

[REDACTED]

[REDACTED]

Listing of all serious adverse events (including IOL repositioning and/or IOL exchange due to IOL misalignment) and adverse device-related events will be presented.

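### Does reporting ≤10° rotational stability as a proportion of pooled eyes, without subject counts or an interval beside it, misstate the result?

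*SAP*

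**What the plan says.** **Allocation.** SAP 1.4: "Subjects will be randomized to either the test #1, test #2, or control IOL on a 1:1:1 basis". Protocol 10.1 adds, for subjects with both eyes eligible, that "both eyes will be implanted with the same lens model". Lens model therefore varies between subjects and never within one.

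**Population.** SAP 2.1 counts every study eye: "All eyes will include both study eyes from bilaterally implanted subjects and one study eye from unilaterally implanted subjects".

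**Endpoint.** Protocol 6.1 defines the primary endpoint as a percentage of eyes, with misalignment of at most 10° from baseline. SAP 5 keeps that unit. It begins "The frequency counts and proportion of eyes with", names the ≤10° category among others that are redacted, and ends "of axis change at all postoperative visits will be reported by lens group". The sentence before it reports absolute axis rotation from the operative visit at every postoperative visit collected.

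**Statistics.** SAP 2.4: "For categorical data, the frequency and proportion will be computed". For continuous variables the same section lists N, mean, SD, median, minimum and maximum.

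**Status of the analysis.** SAP 1: "Due to a much smaller sample size than planned, only descriptive summaries of safety and selected effectiveness endpoints will be presented".

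**Counts.** SAP 3 plans subject accountability by scheduled visit, and a table by IOL with available eyes and the numbers of missing and active subjects.

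**The concern.** Two eyes of one person, operated on with the same lens model, usually by the same surgeon, may behave alike. If they do, 40 eyes from 20 people carry less information than 40 eyes from 40 people. An analysis that randomises people but counts eyes is a familiar source of overstated precision.

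The early stop sharpens the worry. With few subjects per arm, a high stable proportion, or one with no failures at all, rules out less than it seems to. A reader who sees the per-eye figure by lens group, with no subject count or interval beside it, may compare arms and trust the denominator too much. Rotational stability is also the protocol's primary outcome, so this is not a side table.

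**Working it through.** There is no stated figure to reproduce. SAP 6 (sample size) is wholly redacted, and no arm size, bilateral share or inter-eye correlation is visible. The inputs in steps 2 and 3 are assumptions.

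**1. What the plan computes.** The visible output is a count and a proportion of eyes. Neither depends on the correlation between eyes. Take 40 eyes from 20 bilateral subjects, with 2 eyes beyond 10°. The failing proportion is 2/40 = 5.0% whether the two eyes belong to one person or to two. Only a standard error would differ:

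- Eyes treated as independent: √(0.05 × 0.95 / 40) = 0.0345.
- Clustered on subject, both failures in one person: the squared subject residual sums total 1.9² + 19 × 0.1² = 3.80, so the SE is √((20/19) × 3.80 / 40²) = 0.0500.
- Clustered, failures in two people: 2 × 0.9² + 18 × 0.1² = 1.80, so the SE is √((20/19) × 1.80 / 40²) = 0.0344.

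The visible SAP asks for none of these three.

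**2. How large the effect would be if an interval were computed.** Let b be the share of subjects who are bilateral and ρ the inter-eye correlation. The design effect is 1 + 2bρ/(1 + b), and its square root is the factor on the standard error.

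| b | ρ = 0.2 | ρ = 0.5 | ρ = 0.8 |
|---|---|---|---|
| 25% | 1.04 | 1.10 | 1.15 |
| 50% | 1.07 | 1.15 | 1.24 |
| 75% | 1.08 | 1.20 | 1.30 |
| 100% | 1.10 | 1.22 | 1.34 |

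The factor is 1.00 if b = 0 or ρ = 0, and at most √2 = 1.41. A nominal 95% interval that treated eyes as independent would cover about 94% at a design effect of 1.08, 89% at 1.5 and 86% at 1.8.

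For example, take 20 subjects, 15 of them bilateral, so 35 eyes with 90% stable. The Wilson interval is 75.8% to 96.3% with eyes independent. At ρ = 0.5 the design effect is 1 + 2 × 0.75 × 0.5 / 1.75 = 1.43, the effective n is 35/1.43 = 24.5, and the interval is 72.3% to 96.9%.

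**3. The case of no failures.** The upper 95% limit on the failure rate is 1 − 0.025^(1/n), with the effective n inserted.

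- 20 subjects, all bilateral (40 eyes): 8.8% at ρ = 0, 12.9% at ρ = 0.5 (n = 26.7), 16.8% at ρ = 1 (n = 20).
- 20 subjects, 25% bilateral (25 eyes): 13.7% at ρ = 0, 16.2% at ρ = 0.5 (n = 25/1.2 = 20.8).

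These limits are heuristic, since ρ cannot be estimated when every eye is stable. They describe an interval that the visible plan does not contain.

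**4. What else the reader will have.** The eye denominator bounds the number of subjects between half of it and all of it. SAP 3 adds available eyes and missing and active subjects by IOL. SAP 5, read with SAP 2.4, adds the distribution of absolute rotation: its SD and maximum show how near to 10° the eyes came, which a proportion cannot. The proportion is therefore not the only result left on rotation.

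**5. Whether anything is missing.** Redacted lines directly follow the ≤10° sentence in SAP 5. Others stand in SAP 2.4 and around the primary-endpoint analysis in protocol 21.2. An interval, a first-eye summary or a rule for paired eyes would naturally sit there. Their absence from the visible text does not show that the plan lacks them.

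**The case for a change.** The best case for the concern is that descriptive tables are still read inferentially. Results by lens group invite comparison, and 40 of 40 eyes may come from 20 people or from 40. Redaction is also not a complete answer. The SAP 2.4 sentence naming the categorical statistics is complete as it stands, and SAP 2.1 carries no redaction mark, so no one-eye-per-subject population is visible in the SAP's own list. The SAP 3 table does not visibly give the unilateral/bilateral split behind each ≤10° proportion. The remedy would be cheap: a subject count per cell, a clustered interval, and an exact interval on first eyes.

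Part of this stands. The facts about allocation and pooling are right, the arithmetic is right, and no interval is visible for this endpoint. A subject count printed beside each eye count would be a reasonable courtesy to the reader.

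It does not amount to a fault. The redacted lines in SAP 5 are exactly where such detail would go, so the omission remains unproven. Adding intervals would also reverse a deliberate choice to report descriptively after termination. The clustered interval has zero width when every eye is stable, so a second interval on a different denominator would be needed next to it. In a small terminated study, two intervals that cannot be compared directly may confuse as much as they inform.

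**Conclusion.** The concern does not hold. The endpoint is defined per eye, the planned summary is per eye, and the visible plan attaches no precision statement or test to it. The reported counts and proportions will be correct under any inter-eye correlation, so the size of the error in the planned output is zero.

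The factor of 1.04 to 1.34 on interval width (bilateral share 25% to 100%, correlation 0.2 to 0.8, both assumed) applies only to an interval computed as if eyes were independent, and none is visibly planned. If redacted text did contain such an interval, that text would need its own assessment; nothing visible suggests it. What remains is a preference about table layout, with subject information already planned by lens in SAP 3.
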